9 STUDY COMPLETION AND REMUNERATION

At the last scheduled protocol visit a study completion form will be completed, which requires the signatures of both the participant and the investigator. The participants will also be provided with a letter of appreciation.

Once their involvement in the study is complete, participants will be informed about receiving feedback following study completion in the Letter of Appreciation.

Participant remuneration will be \$70 for completing the study for the treatment group and \$80 for the control-treatment group. This reflects a reimbursement rate of \$20 per hour.

10 STATISTICAL ANALYSIS AND DATA MANAGEMENT

10.1 STATISTICAL ANALYSIS

All data will be analyzed by CORE at the University of Waterloo. Descriptive statistics will be provided on information regarding baseline variables (e.g. age, sex). The appropriate tests will be selected based on tests of normality; non-parametric tests will be used for data not showing a normal distribution. Analysis of variables will be conducted separately on each eye, and data will not be pooled. For assessments conducted for each eye separately, the right eye will be used for analysis if there is no difference between eyes.

The following planned comparisons of the key endpoints (SPEED scores, MGS, pre-lens tear break-up time, reported average wear time and comfortable wear time) will be made:

- Within group comparisons:
 - Baseline vs. 1 month [2-sided paired t-test or Wilcoxon signed rank test]
 - For treatment group only: Baseline vs. 1 month vs. 3 month [Repeated measures ANOVA or Friedman test]
 - Baseline vs. 1 month pooled data (i.e. treatment group and control-treatment group after 1 month treatment) [2-sided paired t-test or Wilcoxon signed rank test]
- Between group comparisons:
 - 1 month post-treatment vs. 1 month control (i.e. no treatment) [2-sided independent t-test or Mann-Whitney U test]

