2 OBJECTIVES

The objectives of this clinical trial are:

- To assess eye dryness symptoms (using the SPEED questionnaire) at 1- and 3-months post iLux® treatment;
- To assess Meibomian gland secretions (by expression using the Meibomian Gland Evaluator) at 1- and 3-months post iLux® treatment.

Primary endpoint:

- Changes in SPEED questionnaire score at 1 month.

Secondary endpoints:

- Meibomian gland secretion (assessments will be reported as meibomian gland scores (MGS));
- Pre-lens tear break-up time;
- Reported average wear time and comfortable wear time.

Exploratory endpoint:

- Changes in symptoms, determined using CLDEQ-8 and OSDI questionnaires, at 1- and 3-months, and SPEED at 3 months post iLux® treatment.

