3 NULL HYPOTHESES

- There will be no difference between treatment and control groups for mean comfortable CL wear time.
- There will be no difference between treatment and control groups for symptoms, determined using SPEED questionnaire, at 1-month.
- There will be no difference between treatment and control groups for Meibomian gland score (MGS) at 1-month.

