4.2 STUDY POPULATION

4.2.1 SAMPLE SIZE CALCULATION

There are no current data available regarding the minimally clinically important differences for MGS nor SPEED scores to inform an effect size. Data from Blackie et al³ show a 12-point improvement in MGS score and 8-point improvement in SPEED scores with small standard deviations, corresponding to very large effect sizes of 1.7 and 1.8, respectively. This data supports a minimum sample of 9 in each group would be required to detect an 8-point mean difference in

SPEED scores at 90% power (alpha=0.05, power analysis = a priori, two-tailed, difference between two independent means).

However, an effect size of 1.7 and 1.8 are ambitious targets in this field. Applying targets of a more realistic effect size of 1.0 and a power of 90%, a minimum sample size of 23 in each group is recommended (alpha=0.05, power analysis = a priori, two-tailed, difference between two independent means). Factoring a 10% dropout, the total suggested sample size is 52 participants.

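### Section 10.1 lets an undefined normality check choose the primary SPEED test, so neither the test nor the effect measure is fixed in advance

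*Combined protocol and SAP*

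**What the plan says.** Section 2 gives the primary endpoint as "Changes in SPEED questionnaire score at 1 month". Section 10.1 sets the rule for choosing a test: "The appropriate tests will be selected based on tests of normality; non-parametric tests will be used for data not showing a normal distribution". It then says that "planned comparisons of the key endpoints (SPEED scores, MGS, pre-lens tear break-up time, reported average wear time and comfortable wear time) will be made" and lists each comparison with a parametric and a rank option. The only between-group comparison, and so the only one that uses the randomization, reads "1 month post-treatment vs. 1 month control (i.e. no treatment) [2-sided independent t-test or Mann-Whitney U test".

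Section 4.2.1 plans on "alpha=0.05, power analysis = a priori, two-tailed, difference between two independent means", with an effect size of 1.0, 90% power and 23 per group, or 52 in total after 10% dropout.

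The null hypotheses in section 3 are mixed. For wear time the null is about a mean: "There will be no difference between treatment and control groups for mean comfortable CL wear time". For SPEED no summary measure is named: "There will be no difference between treatment and control groups for symptoms, determined using SPEED questionnaire, at 1-month".

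No other section settles which test is primary. The plan does not say which normality test is used, at what level, or on what (each arm, pooled residuals, raw score or change).

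**The concern.** Naming two tests is not the same as choosing one. Here the choice depends on the outcome data, through a rule with three unspecified parts. Two analysts who follow section 10.1 faithfully could report different primary tests.

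The two branches also answer different questions. The t-test compares means, which is what the sample size is built on. Mann-Whitney compares ranks, and it addresses the mean difference only if the arms differ by a shift. The effect measure behind the primary conclusion is thus left open. Section 10.1 does not commit to a mean difference with a confidence interval on either branch.

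At stake are how clearly the primary result can be interpreted and, when the arms differ in shape, some departure from the nominal error rate or power for the mean hypothesis.

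**Working it through.** **Inputs from the documents.** Two-sided alpha 0.05, effect size 1.0, power 90%, 23 per group, 10% dropout, an 8-point SPEED difference at effect size 1.8 (all section 4.2.1); SPEED range 0–28 (section 4.5.3.2). Implied SPEED SD: 8/1.8 = 4.44.

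**The plan's own figure.** For a two-sample t-test the noncentrality is d√(n/2) = 1.0 × √11.5 = 3.39 on 2 × 23 − 2 = 44 degrees of freedom. Power is 91.2%, and 23 is the smallest n per group that reaches 90%. With dropout, 46/0.90 = 51.1, or 52 when rounded up. The sample size reproduces.

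**Simulating the rule.** 23 per arm. Shapiro-Wilk at 5% in each arm (assumed, since the plan names nothing); if either arm fails, Mann-Whitney, otherwise the t-test. SPEED-like scores are rounded and kept within 0–28. Means and shapes are assumptions; only the SD of 4.44 derives from the plan. In the mixtures, SD means the spread within each subgroup. The mean-based comparator is Student's t in rows marked (t) and Welch otherwise. Rows marked (t) used 20,000 runs and the others 6,000. Monte Carlo standard error at 5% with 6,000 runs is √(0.05 × 0.95/6000) = 0.3 points. Two values in a cell come from separate runs.

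Rejection rate when the means are equal:

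| Scenario | Rule | Mean test |
|---|---|---|
| Identical normal arms (t) | 5.4% | 5.3% |
| Identical SPEED-like arms, SD 4.4 (t) | 5.3% | 5.2% |
| Identical skewed arms, gamma shape 2 (t) | 5.2% | 5.0% |
| 75% of treated 3 points better, 25% 9 points worse, SD 4.44 | 6.2%, 7.1% | 5.1%, 5.6% |
| Same, SD 3.55 (assumed) | 9.2%, 9.5% | 5.5%, 5.8% |
| Exponential-shaped treated arm, SD 4.44 | 7.6%, 7.8% | 5.6% |
| Two tight clusters (75/25) v normal, equal total SD (t) | 8.3% | 5.2% |

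The means cancel in the 75/25 row because 0.75 × 3 = 0.25 × 9 = 2.25.

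Power:

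| Scenario | Rule | Mean test |
|---|---|---|
| SPEED-like, 1 SD shift, SD 4.4 (t) | 91.2% | 91.4% |
| Same shift, treated mean 5, near the floor (t) | 90.8% | 90.9% |
| 30% of treated improve by 10 (mean difference 3.0), SD 4.44 | 41.2%, 40% | 42.7%, 42% |
| Same, SD 3 (assumed) | 50%, 51% | 61% |
| 50% of treated improve by 8, SD 4.44 | 68.8% | 69.2% |
| Exponential in both arms, shift of 3 points | 84.6%, 84% | 63.4%, 65% |
| Gamma-skewed in both arms, shift | 73% | 62% |

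**How often the rule switches.** It switches in about 10% of trials with exactly normal data and in 11–12% with rounded SPEED-like scores. This rises to 37% when the treated arm sits near zero and 84% with gamma skew. If pooled residuals were tested instead of each arm, the normal-data figure would be about 5%. The unspecified target alone therefore changes how often the primary test changes.

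**Reading the tables.** With normal data the switch buys nothing. With identical arms the rule is sound. It departs from 5% only when means match and shapes do not, and by how much depends on the assumed shape and SD. In the last two power rows it outperforms the mean test.

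**The case against.** The strongest reply is that the candidate tests are named in pairs, so the analyst's freedom is narrow, and that the rule does little harm. Much of this stands. If treatment does nothing, the two distributions are the same and the rule holds about 5%. The least favourable figures need SDs below the one that the plan implies. Under a shift in skewed data, the rank branch is the better test.

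The reply does not remove the gap. The selecting rule is still undefined, and the primary comparison still has no fixed effect measure.

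A reader might infer several stronger points that the documents do not support:

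- **That type I error is seriously inflated.** This needs equal means with different shapes, such as harm to a quarter of treated participants that exactly offsets benefit in the rest.
- **That the switch occurs mainly when only some participants respond.** At SD 4.44 the switch rate was 12.9% with half the treated arm improving by 8 points, against 12.4% with no effect. Ordinary skew triggers it far more often.
- **That the analyst would pick the favourable test.** Section 4.1.3 declares the study unmasked, but nothing in the plan suggests such selection. Even free choice of the better test would give about 5.9–6.4% when the arms are identical.
- **That the primary null is stated as a mean.** Only the wear-time null is. For SPEED the mean basis comes from section 4.2.1.
- **That the normality rule causes the missing estimate.** The t-test branch promises none either. The remark in section 4.2.1 that no minimally important difference is available concerns planning the effect size, not interpreting a p-value.
- **That every questionnaire is covered explicitly.** CLDEQ-8 and OSDI are not among the listed key endpoints; they fall under the general sentence only.

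**Conclusion.** The point holds as a prespecification gap. The primary between-group test is left to a data-dependent rule that is not fully defined, while the sample size rests on "two-tailed, difference between two independent means". The sample size itself is correct.

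The numerical effect is modest. For the mean hypothesis, false rejection is about 5% with identical arms. For the mixed-response shape it is about 6–7% at SD 4.44 and 9–10% at an assumed SD of 3.55; the other equal-mean shapes tried gave 7.6–8.3%. Power loss against partial response is about 1–2 points at SD 4.44 and about 10 points at an assumed SD of 3. All of this assumes Shapiro-Wilk at 5% in each arm, and that 8/1.8 is a fair SD for the quantity analysed, which the plan does not define.

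This is a cheap improvement, not a defect that threatens the trial's conclusions.

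**What to change.** In section 10.1, delete the normality-based selection and make these changes:

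- **Primary analysis.** Name one comparison of mean 1-month change in SPEED between the randomized groups, for example a Welch t-test or ANCOVA adjusted for baseline SPEED. Report the mean difference with its 95% CI in SPEED points.
- **Other key endpoints.** Treat the between-group comparison in the same way, each in its own units. Use a paired mean comparison within groups, and repeated measures ANOVA for the three-timepoint comparison in the treatment group.
- **Rank tests.** Keep Mann-Whitney, Wilcoxon and Friedman as named sensitivity analyses that do not replace the primary result.

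The cost is wording only. Visits, data and sample size do not change: 23 per group still gives 91.2% power for the planned t-test.

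The downside is real. If scores are skewed in both arms and treatment acts as a shift, the mean-based test can lose about 10–20 points of power against the rank test (84% v 65% and 73% v 62% under the assumed shapes). The sensitivity analysis would show this.

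Fixing the rank test instead would also close the gap. It gives about 89.3% power with 23 per group on normal data, it would need its own stated effect measure, and it would part from the mean basis of section 4.2.1.

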4.4.3 TREATMENT GROUP

4.4.3.1 ILUX® TREATMENT (VISIT 2A)

Visit 2 occurs immediately after Visit 1 for participants that have been randomized to the treatment group. The following procedures will be conducted:

1. The participant will remove their contact lenses.
2. The participant's eyelids will be cleaned by the investigator.
3. The iLux® treatment will be administered to both eyes by the investigator.
4. A slit lamp biomicroscope examination will be performed as a safety check.
5. The participant will be provided with verbal and written instructions on how to complete blinking exercises. One round of blinking exercises will be completed with the investigator to ensure the participant understands the instructions.
6. Monocular & binocular distance logMAR visual acuity (high contrast, high illumination) with habitual spectacles as a safety check.

4.4.3.2 1 MONTH FOLLOW-UP (VISIT 3A)

Participants will attend this visit 23-37 days after iLux® treatment administered at Visit 2. Participants will attend this visit wearing a new pair of their habitual CLs for ≥ 4 hours prior to the visit. Participants who attend not meeting this criteria will be rescheduled (unless they report problems when wearing their lenses). The following procedures will be conducted:

1. Review medical history (changes in medication, adverse events)
2. Collect information on participant's CL wear habits:
 - a. Average total wear time (number of days per week, number of hours per day)

- b. Average comfortable wear time (number of hours per day).
3. The participant will complete the CLDEQ-8 questionnaire, SPEED questionnaire and OSDI questionnaire.
4. Monocular & binocular distance logMAR visual acuity (high contrast, high illumination) with habitual CLs.
5. Assess pre-lens tear film break-up time.
6. The participant will remove their CLs.
7. Meibomian gland secretion assessment using the Meibomian gland evaluator.
8. Ocular health assessment including ocular surface staining.
9. The participant will be allowed to reapply their habitual CLs or wear their own spectacles. Monocular & binocular distance logMAR visual acuity (high contrast, high illumination) with visual correction.

4.4.3.3 3 MONTH FOLLOW-UP VISIT AND STUDY EXIT (VISIT 4A)

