4.5.12 ILUX® TREATMENT

The upper and lower eyelids of both eyes will be treated with the iLux device using a single disposable Smart Tip. Each eyelid will be divided into two treatment zones: nasal-central, central-temporal. Each zone will be treated for all eyelids of both eyes. The same procedure is applied for each zone. A new Smart Tip will be used for each new participant. One drop of Alcaine (0.5% proparacaine hydrochloride) will be instilled to each eye immediately before iLux® treatment.

The following steps will be taken:

1. With the participant reclined, instruct the participant to look up (if treating the lower lids) or down (if treating the upper lids).
2. Slide the inner pad behind the eyelid positioned to the treatment zone. Confirm the appropriate position by looking through the magnification panel of the device.
3. Slide the Heater Control Switch forward to slide the outer pad gently hold the eyelid in position and deliver heat to the treatment zone.
4. Deliver heat to the treatment zone for 40-90 seconds (indicated by the “melting time” value on the screen display) while looking through the magnifying lens. The duration of heat application is dependent on the quantity of meibum expressed from the glands in the treatment zone.
5. After the application of heat, slide the Heater Control Switch to deactivate the heating LED lights and to move the device to the expression phase.
6. Perform 4 rounds of compression, lasting 5 seconds each. Keep visualizing the quantity and quality of meibum expressed from the glands.
7. Gently remove the inner pad from the eyelid and repeat the process on the remaining treatment zones for each eyelid.
8. Participants will be instructed that they can resume contact lens wear one hour after completion of iLux® treatment unless there is an adverse event, as determined by the investigator and participant. In the case of an adverse event (e.g. ocular surface irritation,

inflammation or discomfort), participants will be advised when to resume contact lens wear following resolution of the event.

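### Eye-level endpoints (MGS, pre-lens break-up time) rest on one eye under an undefined rule; a two-eye mean per participant would give one result and more precision

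*Combined protocol and SAP*

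**What the plan says.** Two adjacent sentences in section 10.1 govern the endpoints measured on each eye. The first is "Analysis of variables will be conducted separately on each eye, and data will not be pooled". The second is "For assessments conducted for each eye separately, the right eye will be used for analysis if there is no difference between eyes". Of the key endpoints listed there, only MGS and pre-lens tear break-up time are measured per eye. SPEED and the two wear times have one value per participant.

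Section 3 states one hypothesis for MGS and names no eye: "There will be no difference between treatment and control groups for Meibomian gland score (MGS) at 1-month". Section 2 lists MGS and pre-lens break-up time as secondary endpoints; the primary endpoint is "Changes in SPEED questionnaire score at 1 month".

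Treatment is bilateral (sections 4.1.1 and 4.5.12): "The upper and lower eyelids of both eyes will be treated with the iLux device". Eligibility sets an MGS limit that both eyes must meet (sections 4.2.3 and 4.5.7). The follow-up procedure lists (sections 4.4.3.2 to 4.4.4.2) say only "Meibomian gland secretion assessment using the Meibomian gland evaluator", without naming the eyes. Sections 4.5.5 and 4.5.7 describe the measurements but give no rule for combining eyes.

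**The concern.** There are two defects.

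- **The result is not determined in advance.** The right-eye rule depends on the eyes not differing, but the plan does not say how that is judged: by which test or margin, on which variable, at which visit, or in which group. If they do differ, the preceding sentence leaves a right-eye and a left-eye analysis, and nothing says which one answers the MGS hypothesis. The choice could then be made after the data are seen, in a trial that section 4.1.3 describes as having no masking.
- **Information is discarded.** Both eyes of a participant receive the same allocation, and section 10.1 implies that both are measured. Under the right-eye branch only one contributes, so the MGS and break-up time estimates are less precise than the data allow.

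**Working it through.** **Inputs from the plan.** Section 4.2.1 gives two-sided alpha 0.05 and "a more realistic effect size of 1.0 and a power of 90%, a minimum sample size of 23 in each group". For MGS it cites "a 12-point improvement in MGS score and 8-point improvement in SPEED scores with small standard deviations", with effect sizes of 1.7 (MGS) and 1.8 (SPEED).

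**Assumptions.** The correlation between eyes, ρ, is not in the documents; 0.5, 0.7 and 0.9 are used. Both eyes are taken to have equal variance and the same treatment effect. The MGS standard deviation is back-calculated as 12/1.7 = 7.06 points and assumed to be per eye.

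**Reproducing the plan's figure.** For a two-sample t-test with effect size 1.0, the noncentral t distribution gives power 0.9125 at 23 per group and 0.8997 at 22. So 23 per group is right for 90% power. With 10% dropout, 46/0.9 = 51.1, rounded up to 52.

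**Two-eye mean.** Relative to one eye, the variance of the mean is (1+ρ)/2. The standardised effect becomes 1/√((1+ρ)/2), and the equivalent gain in participants is 2/(1+ρ) − 1. The 95% CI half-width for one eye is t(0.975, 44) × √(2/23) × SD = 2.015 × 0.2949 × 7.06 = 4.20 points. For the mean it is multiplied by √((1+ρ)/2).

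| | One eye | ρ = 0.5 | ρ = 0.7 | ρ = 0.9 |
|---|---|---|---|---|
| Variance ratio | 1 | 0.75 | 0.85 | 0.95 |
| Worth in extra participants | – | 33% | 18% | 5% |
| Standardised effect | 1.000 | 1.155 | 1.085 | 1.026 |
| Power, 23 per group | 91.2% | 96.9% | 94.9% | 92.5% |
| n per group for 90% power | 23 | 17 | 19 | 21 |
| MGS 95% CI half-width (points) | 4.20 | 3.63 | 3.87 | 4.09 |

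At the effect size of 1.7 cited for MGS, one eye at 23 per group already has more than 99.9% power. There the gain is interval width only.

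**Separate-eye branch.** These figures come from simulation with bivariate normal eyes and 23 per group.

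| | ρ = 0.5 | ρ = 0.7 | ρ = 0.9 |
|---|---|---|---|
| Right and left tests disagree at p < 0.05, effect 1.0 | 12% | 10% | 6% |
| Same, effect 0.6 | 34% | 26% | 15% |
| Type I error if either eye may be claimed | 9.0% | 8.2% | 7.1% |

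The right-eye test alone keeps its type I error at about 5%.

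**How often that branch is entered.** This depends on the missing definition. Suppose it is a paired t-test at 0.05 on 46 completers.

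- If the eyes are truly equal, the branch is entered about 5% of the time. Entry together with disagreement (effect 1.0) then occurs in about 0.6%, 0.4% and 0.3% of trials. Type I error under the whole rule, with either eye claimable in that branch, is 5.0% to 5.2%.
- If the eyes differ by a constant 0.3 SD, the branch is entered with probability 0.51, 0.73 or 0.99. A constant difference does not change the disagreement rate, because each test compares groups within one eye. Entry together with disagreement is then roughly 0.51 × 12%, 0.73 × 10% and 0.99 × 6%, or 6% to 7% of trials.

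**The case against.** The strongest reply is that little is at risk. A right-eye analysis is valid and common practice, only secondary endpoints are involved, and one eye already meets the 90% target at effect size 1.0. The precision gain rests on a correlation that the documents do not give. The point figures also rest on a standard deviation inferred from a cited study, which may not be per eye. At ρ = 0.9 the gain is 0.1 points on a half-width of 4.2. If the eyes are truly equal, the separate-eye branch is rarely entered, and at an effect of 1.7 the two eyes almost never disagree (about 0.02% of trials). The plan does provide a fallback, which is to analyse each eye. Using the right eye unconditionally would remove the ambiguity by deleting one condition, and would keep the no-pooling choice.

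Most of this stands as a limit on size. It does not remove the point. The undefined condition and the undesignated result do not depend on ρ or on the standard deviation. An unconditional right-eye rule would cure the ambiguity but would still discard the other eye. A mixed model with participant as a random effect would also work; the two-eye mean is simpler and goes straight into the tests already listed.

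**Conclusion.** The concern holds and the change should be made. For MGS and pre-lens break-up time, the plan does not fix which analysis will be reported, and its default discards one eye of a bilaterally treated participant. At effect size 1.0, the two-eye mean adds about 6, 4 or 1 percentage points of power at ρ = 0.5, 0.7 or 0.9, and takes about 0.6, 0.3 or 0.1 points off the MGS half-width. This assumes equal variances, a common effect in both eyes and, for the point figures, a per-eye standard deviation of 7.06. Alpha inflation is negligible if the eyes are truly equal, so the main harm there is lost precision. The undetermined result matters more if the eyes differ. The primary analysis and the sample size do not change.

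**What to change.** Replace both eye-handling sentences in section 10.1 with:

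> For MGS and pre-lens tear break-up time, the participant's value at each visit is the mean of the two eyes (the available eye if one is missing). The participant is the unit of analysis. Right-eye and left-eye results are descriptive.

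This drops the conditional comparison of eyes. The mean can be used directly in the t-tests, rank tests and repeated-measures tests already listed. Also state in the visit procedures that both eyes are measured at follow-up for these two endpoints.

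The cost is two replaced sentences and one clarification. No extra measurements are needed if both eyes are already assessed at follow-up, as section 10.1 implies; the visit lists do not confirm this, so it should be checked first.

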4 MATERIALS AND METHODS

4.1 STUDY DESIGN

4.1.1 OVERALL DESIGN

This is a prospective, single-site, parallel-group study involving 52 existing CL wearers who have confirmed EDE (according to the TFOS DEWS II diagnostic criteria). This study will involve three visits (Figure 1). Participants will attend CORE for a total of 3.5 hours.

Eligible participants will be randomized in a 1:1 ratio to receive a single, bilateral iLux® treatment at Visit 1 (treatment group), or delayed iLux® treatment provided at Visit 2 (control-treatment group i.e. 1-month no treatment, administer treatment at Visit 2). The treatment group will be reviewed 1- and 3-months after treatment. The control-treatment group will be reviewed at 1-month, at which point they will receive a single, bilateral iLux® treatment. The control-treatment group will be reviewed 1 month (full clinical assessment, including symptom assessment) and 3 months (symptom assessment only) after iLux® treatment. Participants randomized to the treatment group will be involved in the study for 3 months. Participants randomized to the control-treatment group will be involved in the study for 4 months.

Participants will wear their habitual CLs during the study. To ensure compliance, they will be supplied their habitual CLs and, if applicable, their habitual lens care products, for use during their involvement in the study.

[figure not shown]

Figure 1: Study flow chart

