4.2.4 REPEATED SCREENINGS

In some circumstances, a repeated screening may need to be scheduled. Examples include, but are not limited to:

1. The participant attends having used any ocular lubricants (including artificial tears, emollients or liposomal sprays), used eye make-up or facial cosmetics around their eyes, rubbed their eyes and has been swimming in a chlorinated pool less than 12 hours prior to attending the screening visit;
2. Incomplete information available at time of screening to determine eligibility (e.g. current lens brands worn, history from current eye care practitioner etc.)
3. Study procedures unable to be completed in time scheduled for visit;
4. Study products not available at the time of the screening visit;

5. A transient health condition which may affect the eye(s) (e.g. a common cold, active allergies, fatigue etc.)
6. The short term use of medications (e.g. antibiotics, antihistamines etc.)
7. Reassessment of baseline ocular conditions (e.g. corneal and/or conjunctival staining, scars etc.)

The maximum total number of screenings permitted per participant will be 3.

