4.5.7 MEIBOMIAN GLAND SECRETION ASSESSMENT

Meibomian gland dysfunction results in stagnation of the meibum (oil) within the glands. The ease of expression of the gland and the quality of the expressed contents therefore provides an indication of the functional capabilities of the glands. The MG Evaluator (TearScience/J&J) will be used to apply a pressure of 1.2g/mm² to the lower eyelid just inferior to the lid margin in three areas – nasal, central and temporal. Five consecutive glands in each area will be assessed for expressibility. Glands will be graded as follows: 0: No secretion (includes capped orifices), 1: inspissated (toothpaste), 2: colored/cloudy with debris, 3: clear liquid oil. The results for each location will be summed (Meibomian gland secretion score, MGS, range = 0 to 45). A score of ≤ 15 (on a scale of 0 to 45) for 15 glands of the lower lid in both eyes is required to be eligible for this study. In addition, the total number of functional Meibomian glands, defined as having a liquid section with a grade 2 or 3, will be counted (range = 0 to 15).

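### The only 3-month test is a one-arm, three-level omnibus test that cannot show whether the 1-month gain lasts; for MGS, pre/post tests are also inflated by regression to the mean

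*Combined protocol and SAP*

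**What the plan says.** Section 2 sets two objectives, each with a 3-month part: "To assess eye dryness symptoms (using the SPEED questionnaire) at 1- and 3-months post iLux" treatment, and "To assess Meibomian gland secretions (by expression using the Meibomian Gland Evaluator) at 1- and 3-months post iLux" treatment. The same section makes 1-month SPEED the primary endpoint and lists 3-month SPEED as exploratory. Section 3 states the SPEED and MGS null hypotheses at 1 month only.

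Section 4.1.1 limits the untreated period: "The control-treatment group will be reviewed at 1-month, at which point they will receive a single, bilateral iLux® treatment".

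Section 10.1 names five key endpoints: SPEED, MGS, pre-lens tear break-up time, average wear time and comfortable wear time. The only planned comparison with 3-month data is "For treatment group only: Baseline vs. 1 month vs. 3 month [Repeated measures ANOVA or Friedman test". No follow-up contrast is named. The other within-group tests are a paired baseline to 1-month test and a pooled version that adds the control-treatment group after its own treatment. The single between-group test is at 1 month.

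MGS is also an entry criterion. Section 4.5.7 says: "A score of ≤ 15 (on a scale of 0 to 45) for 15 glands of the lower lid in both eyes is required". Section 4.4.2 treats the screening visit as the baseline visit, and the treatment group goes straight from it to iLux, so there is no second pre-treatment reading in that group.

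**The concern.** There are two separate problems.

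First, a three-level repeated-measures ANOVA or Friedman test asks whether baseline, 1 month and 3 months differ in any way. A large step from baseline to 1 month is enough for significance, whatever happens later. The test therefore does not say whether a benefit is still present at 3 months, for any of the five endpoints. With no untreated group after month 1, it also cannot separate treatment from natural course.

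Second, a score admitted because it was low tends to be higher when measured again, with no treatment at all. For MGS the admitting reading is also the baseline, so the one-arm pre/post tests do not have a 5% error rate under no treatment effect.

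At stake is the reading of the 3-month and pooled results. Section 10.1 lists them beside the randomized comparison, with no ranking and no limit on interpretation.

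**Working it through.** **Sample size used below.** Section 4.2.1 gives 23 per group for d = 1.0, 90% power and two-sided alpha 0.05. This reproduces: the noncentral t gives power 0.912 at 23 and 0.8997 at 22. With 10% dropout, 46/0.9 = 51.1, rounded up to 52. The checks use n = 23 (treatment group) and n = 46 (pooled).

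**Omnibus test when the gain is lost.** Let the true means be 0, g, 0 in SD units at baseline, 1 month and 3 months, with test-retest correlation ρ = 0.7 (assumed; the documents give none).
- Noncentrality: λ = n × Σ(mean − grand mean)² / (1 − ρ) = 23 × (2/3)g² / 0.3.
- g = 0.5: λ = 23 × 0.1667 / 0.3 = 12.8. On F with 2 and 44 degrees of freedom, the rejection probability is about 88%.
- g = 1.0: λ = 23 × 0.6667 / 0.3 = 51.1. The rejection probability is essentially 100%.

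Simulation agrees (88% to 89%, and 100%). The test is almost always significant although nothing remains at 3 months.

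**Regression to the mean in MGS.** The documents give neither the unselected MGS distribution nor its reliability. Assumptions: source-population mean 12 to 20, SD 8, inter-eye correlation 0.5, test-retest correlation 0.6 to 0.8, normal scores, no treatment effect. Select people with both eyes at 15 or below, then re-measure the right eye with its true score unchanged. The pooled test is shown under both possible baselines for controls.

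| Case (mean, test-retest correlation) | Untreated rise, points | Paired test, n = 23 | Pooled, n = 46, all baselines Visit 1 | Pooled, n = 46, controls' baseline Visit 2B |
|---|---|---|---|---|
| 12, 0.8 | 0.7 | about 10% | about 15% | about 8% |
| 16, 0.7 | 1.6 | about 24% | about 44% | about 13% |
| 20, 0.6 | 2.9 | about 51% to 53% | about 82% | about 27% |

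The percentages are rejection rates of a nominal 5% test. Repeat runs differ by one or two points.

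**Hand check with a simpler model.** For one eye, cut-off at the population mean and reliability 0.8, the expected rise is (1 − 0.8) × √(2/π) = 0.2 × 0.798 = 0.16 SD. Section 4.2.1 implies an MGS SD of 12/1.7 = 7.1, so the rise is 0.16 × 7.1 = 1.1 points. In simulation the three-level ANOVA then rejects in about 21% of trials at n = 23, while the 1-month between-group test stays at about 5%.

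**Size against the planned effect.** The mid-case rise of 1.6 points is 1.6/12 = 13% of the 12-point MGS improvement cited in section 4.2.1, and about 22% of the roughly 7.1 points that d = 1.0 implies.

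**Which endpoints are affected.** The omnibus problem applies to all five. Direct selection toward improvement applies to MGS only. SPEED is not in section 4.2.3. The wear-time criterion there is a lower limit, so it does not create spurious improvement.

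**The case against.** The strongest reply is that the plan's inference already sits at 1 month. The primary endpoint and the SPEED and MGS hypotheses are at 1 month, 3-month SPEED is exploratory, and the objectives say only that outcomes will be assessed. The one between-group test is randomized, and both arms pass the same entry rule, so regression to the mean does not bias it. All of this stands and limits the point to the non-primary results. It does not rescue the 3-month test, which cannot describe 3-month status even as an assessment, and section 10.1 does not call the within-group tests descriptive.

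The magnitudes rest on assumed inputs, and the normal model ignores the 0 to 45 bounds of MGS. That also stands: the figures show a range, not an estimate.

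Some stronger readings are tempting but not supported.
- A reader might infer that all tested outcomes are selected on extreme scores. OSDI and CLDEQ-8 are entry thresholds, but section 10.1 plans no test of them. Any regression in SPEED is indirect, through correlation with the entry scores, and could be small.
- A reader might take the highest pooled error rates as given. They hold only if the controls' baseline is Visit 1, and section 10.1 does not say which visit it is.
- A reader might see the allowance for three screenings (section 4.2.4) as re-testing until a score qualifies. The examples there are mostly logistical or transient, and failing a score threshold is not among them, although the list is open.

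**Conclusion.** The point holds in this form. The 3-month part of both objectives rests on a one-arm omnibus test that does not answer whether a benefit lasts, for any key endpoint. At n = 23 and an assumed correlation of 0.7, it is significant in about 88% to 100% of trials in which a 0.5 to 1 SD gain has vanished by 3 months. That defect does not depend on regression to the mean.

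For MGS alone, selection at Visit 1 adds an expected untreated rise of about 0.7 to 2.9 points under the stated assumptions. This takes the error rate of a paired test to about 10% to 53% at n = 23. For the pooled test it is about 15% to 82%, or about 8% to 27% if controls start from Visit 2B. The randomized 1-month comparison, and with it the primary endpoint, is not affected.

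**What to change.** Change section 10.1 as follows.

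1. For the 3-month objective, replace the three-level test with the paired 3-month minus 1-month change in the treatment group, with a confidence interval. Both visits follow selection and are attended after at least 4 hours of lens wear, whereas Visit 1 follows at least 12 hours without lenses. Describe the result as uncontrolled. Note that section 4.5.13 prescribes the blinking exercises only until the 1-month visit, so the change also spans their end. State that a non-significant result is not proof of persistence.
2. State whether the control-treatment group's baseline in the pooled test is Visit 1 or Visit 2B. Report that group's untreated change from Visit 1 to Visit 2B, with a confidence interval, beside the within-group and pooled changes. Do not subtract it from the 3-month change: it covers one month and is not time-matched.
3. State that efficacy is concluded only from the randomized 1-month between-group comparison, and that within-group, pooled and 3-month p-values are descriptive.

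The cost is wording only, since every measurement is already scheduled. The downside is that the sponsor cannot claim 3-month efficacy from a one-arm p-value.
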